6.3.4.1. Main Analysis

- Estimand strategy: Composite (Section 2.1.3).
- Analysis set: Evaluable (Section 4). All randomized participants who take at least 1 dose
 of investigational product who have provided evaluable baseline data for the endpoint
 (i.e. baseline biopsy data).
- Analysis methodology: For assessing dose response, the proportion of responders at
 Week 48 (defined as the proportion of participants with worsening of fibrosis by ≥1 stage
 and worsening of ≥2 points in Total NAS on liver biopsy, as assessed by sponsor
 identified central pathologist(s), at Week 48) will be analyzed using a Bayesian Emax
 dose-response model. For assessing pairwise comparisons, the proportion of responders
 at Week 48 will be analyzed using logistic regression models with treatment and baseline
 fibrosis stage (F2/F3) as factors (Section 5.2.1).
- Intercurrent events and missing data: If a participant discontinues treatment or from the study due to lack of efficacy or toleration prior to Week 48 or if they do not have evaluable Week 48 biopsy data, they will be considered to be a responder (as this assumes that these participants will also have worsened). If a participant has improved or maintained the same level of fibrosis compared to baseline, then that participant will be termed as a non-responder.
- If they withdraw from treatment for other reasons (not related to lack of efficacy or toleration) and have evaluable data at withdrawal or Week 48, these data will be utilized to determine whether they are a responder or not.

- The number and proportion of responders for this endpoint at Week 48 will be presented for each treatment arm.
- The model-estimated proportion of responders (and 90% credible interval) for each
 treatment arm, and the placebo-adjusted proportion of responders for BID each dose (and
 90% credible interval), and odds ratio and risk difference (and corresponding 90%
 confidence interval) for other treatment comparisons will be presented at Week 48. For
 comparisons of DGAT2i+ACCi BID doses vs corresponding DGAT2i BID monotherapy
 doses corresponding 50% confidence interval will also be provided.

6.3.5. Proportion of participants with Worsening of ≥2 points in Total NAS (defined as an increase of at least 2 points in Total NAS compared to baseline) independent of changes in fibrosis at Week 48

6.3.5.1. Main Analysis

- Estimand strategy: Composite (Section 2.1.3).
- Analysis set: Evaluable (Section 4). All randomized participants who take at least 1 dose
 of investigational product who have provided evaluable baseline data for the endpoint
 (i.e. baseline biopsy data).
- Analysis methodology: For assessing dose response, the proportion of responders at Week 48 (defined as the proportion of participants with worsening of ≥2 points in Total NAS independent of changes in fibrosis, on liver biopsy, as assessed by sponsor identified central pathologist(s), at Week 48) will be analyzed using a Bayesian Emax dose-response model. For assessing pairwise comparisons, the proportion of responders at Week 48 will be analyzed using logistic regression models with treatment and baseline fibrosis stage (F2/F3) as factors (Section 5.2.1).
- Intercurrent events and missing data: If a participant discontinues treatment or from the study due to lack of efficacy or toleration prior to Week 48 or if they do not have evaluable Week 48 biopsy data, they will be considered to be a responder (as this assumes that these participants will also have worsened). If a participant's Total NAS has improved or stayed the same compared to baseline, then that participant will be termed as a non-responder. If they withdraw from treatment for other reasons (not related to lack of efficacy or toleration) and have evaluable data at withdrawal or Week 48, these data will be utilized to determine whether they are a responder or not.
- The number and proportion of responders for this endpoint at Week 48 will be presented for each treatment arm.
- The model-estimated proportion of responders (and 90% credible interval) for each treatment arm, and the placebo-adjusted proportion of responders for BID each dose (and 90% credible interval), and odds ratio and risk difference (and corresponding 90% confidence interval) for other treatment comparisons will be presented at Week 48. For

comparisons of DGAT2i+ACCi BID doses vs corresponding DGAT2i BID monotherapy doses corresponding 50% confidence interval will also be provided.

- Change from baseline, over time to Week 48 in fatigue, sleep disturbance, and daytime sleepiness questions from the NASH Symptom Diary
- Change from baseline, over time to Week 48 in fatigue as measured by PROMIS Fatigue questionnaire
- Change from baseline, over time to Week 48 in HRQoL sub-scale scores as measured by NASH-Check
- Change from baseline, over time to Week 48 in PGI-S
- Absolute score over time in PGI-S
- Absolute score over time in PGI-C

6.3.6.1. Main Analysis

- Estimand strategy: Not applicable
- Analysis set: Evaluable (Section 4). All randomized participants who take at least 1 dose
 of investigational product who have provided baseline data for the endpoint, and in
 addition have at least 1 evaluable data point post randomization.
- Analysis methodology: A MMRM will be used for the analysis of continuous endpoints
 with more than one post-baseline collection time point. The MMRM analysis will be
 performed with treatment, study week (nominal timepoint) and treatment-by-study week
 interaction as fixed effects, and baseline fibrosis stage (F2/F3) as a factor and baseline
 value of the analysis endpoint as a covariate. If the endpoint being analyzed is logtransformed (i.e. for all percentage changes from baseline in continuous endpoints which
 will be derived from the analysis of log-transformed relative changes from baseline), the
 baseline value of the analysis endpoint will also be log-transformed. Repeated measures
 model with unstructured covariance matrix will be utilized (Section 5.2.2).
- Intercurrent events and missing data: All observed data collected during the postbaseline treatment period will be utilized. Missing data will not be explicitly imputed.

- The sample size, mean, standard deviation, median, minimum, and maximum at the baseline and postbaseline visits for observed values and relative and absolute change from baseline will be presented for each treatment arm.
 - Box and whisker plots by randomized arm and by week will also be displayed to characterize the distribution of percent changes from baseline over time.
- For percentage changes from baseline the model-estimated mean relative changes for
 each treatment comparison and the corresponding 90% CI will be obtained from the
 model. The mean relative changes (RC) and their CIs will be exponentiated and percent
 change will then be determined as follows: Percent change = 100* (RC 1). For
 comparisons of DGAT2i + ACCi BID doses vs corresponding DGAT2i BID
 monotherapy doses corresponding 50% confidence intervals will also be provided.
- CCI
 permit retrospective analysis of CCI
)
 - These results may or may not be generated in the context of the present study.

6.3.7. Event-based Tertiary/Exploratory Endpoints

6.3.7.1. Main Analysis

The following endpoints will be summarized descriptively by treatment group (Section 5.2.4) for randomized participants, separately for pre-randomization events and treatment-emergent events (as SAEs will be collected prior to randomization so could also be sent for adjudication):

 Occurrence of any one of the following over time up to Week 48 based on final adjudication:

Deaths

- All cause mortality (deaths regardless of cause)
- Death due to Myocardial Infarction
- Death due to Cerebrovascular Accident
- Death due to Hepatic failure

For non-fatal events.

- Cardiovascular events
 - Myocardial infarction

- Cerebrovascular event (stroke) or transient ischaemic attack
- Hospitalizations due to unstable angina
- Hospitalization for heart failure

Liver events

- Hepatic encephalopathy
- Upper Gastrointestinal bleed due to portal hypertension
- Liver transplant evaluation
- New diagnosis of hepatocellular carcinoma
- Ascites
- Acute kidney injury due to hepatorenal syndrome
- Drug induced liver injury
- Increase of Model of end-stage liver disease (MELD) score from ≤12 to ≥15 indicating listing for liver transplant (See Appendix 2.4.2)

6.3.8. Pharmacokinetic (PK) Endpoints

6.3.8.1. Main Analysis

concentration data will be listed and summarized by treatment group, visit and nominal timepoint for DGAT2i and ACCi separately.

As a general rule, samples collected in those assigned placebo will not undergo analysis for DGAT2i and ACCi. However, when analysis is undertaken, for example: for cases of quality issues at selected site(s), PK results will be listed.

Any samples that have been recorded with a status of 'Label information and paperwork disagree' will be excluded from any PK summaries, as these samples are considered to be unreliable with the sample details at the analyzing laboratory not matching sites' source documents.

6.4. Subset Analyses

To evaluate the effect of treatment on liver fat and liver volume as assessed by MRI-PDFF, these imaging endpoints will only be analyzed in the subset of participants included in the Imaging substudy population. The analysis of these endpoints is included in Sections 6.2.5 and 6.3.6.

The following subset analysis will also be performed:

Analysis of glycemic endpoints in the Type 2 diabetes mellitus (T2DM) population

6.5. Baseline and Other Summaries and Analyses

Summaries that account for all participants who offered at least consent for pre-qualification and whether screen failed or randomized will be presented.

6.5.1. Baseline Summaries

Demographic and other baseline characteristics such as participant age, gender, weight, body mass index (BMI), waist circumference, region, stratification factors, ethnicity and race, will be summarized by randomized arm.

For each efficacy endpoint (ie primary, secondary or tertiary endpoint), baseline values will be listed and descriptively summarized by randomized arm.

6.5.2. Study Conduct and Participant Disposition

The number of participants randomized, treated, completing and discontinuing study medication and from the study, will be summarized by randomized arm. For participants who did not complete study medication or the study, the reasons for withdrawal will be presented.

6.5.3. Study Treatment Exposure

The number of days of study treatment exposure will be summarized by randomized treatment group and number of participants with ≤ 8 weeks, > 8 to 24 weeks, > 24 to 36 weeks, > 36 to 48 weeks (+4 days – to allow for the maximum window for administration of study treatment), and > 48 weeks (+5 days) exposure respectively. The formula to compute compliance is defined in Appendix 2.5. Overall compliance (Day 1 to Week 48 or premature termination during treatment phase) will be summarized using descriptive summary statistics and by frequency n (%) in the following two categories by randomized arm:

- o <50%
- ≥50 and < 80%, inclusive
- o ≥80%

6.5.4. Medical History

The number and proportion of participants with each of the up to 12 prespecified medical histories will be summarized by randomized treatment group. In addition, the

number of participants with 0, 1, 2, 3, 4, 5, 6, 7, 8 or >8 of these prespecified medical histories will be summarized.

6.5.5. Concomitant Medications and Nondrug Treatments

The number and proportion of participants taking specific concomitant medications for medical histories on Day 1 and as concomitant medications at the end of treatment/Week 48 will be summarized by randomized treatment group, separately for each specific medical history. In addition, the number and proportion of participants who have increased or decreased their dose of these medications will also be summarized by randomized treatment group, and the number of participants with 0, 1, 2, 3, 4, 5 or >5 of these specific medications will be summarized. All other concomitant medications will be summarized by randomized treatment group.

6.6. Safety Summaries and Analyses

All safety analyses will be performed on the safety population. These will be presented in tabular and/or graphical format and summarized descriptively and will follow Pfizer standards as appropriate. Further details are provided below.

6.6.1. Adverse Events

MedDRA will be used to classify all AEs with respect to system organ class and preferred term. Summaries of AEs will include treatment-emergent AEs according to treatment group.

Furthermore, a 3-tier approach will be used to summarize AEs. Tier-1 consists of prespecified adverse events and will include AEs or collections of AEs related to identified adverse drug reactions in this program related to either DGAT2i or ACCi. Where available, standard MedDRA queries will be used to pool different AE terms that are related to the Tier-1 AEs. The precise AE terms that will contribute to the Tier-1 endpoints will be determined prior to unblinding. For these events, the percentage of participants with incident AE, the risk difference (using an unconditional exact test to compare each active treatment arm vs placebo), its 95% confidence interval, and p-value will be provided. The confidence intervals and p-values are not adjusted for multiplicity and are provided for screening purposes only.

Tier-2 AEs are those that are not Tier-1, but are common, occurring in at least 4 participants in any treatment arm. The cut-off of at least 4 events was chosen because the 95% confidence interval for the between-group difference in percent incidence will always include zero when treatment groups of equal size each have less than 4 events and so adds little to the interpretation of potentially meaningful differences. For these events, the percentage of participants with incident AE, the risk difference and its 95% confidence interval will be provided. The CIs are for estimation purposes only.

For Tier 1 and Tier 2 AEs, TEAEs, by preferred term, will be sorted in descending point estimate of risk difference. For table/graphic output, the following footnotes will be included to provide proper interpretation of p-values and/or confidence intervals, and to describe how comparison is conducted. E.g. P-values and confidence intervals are not adjusted for multiplicity

and should be used for screening purpose only. 95% Confidence intervals are provided to help gauge the precision of the estimates for Risk Difference. Risk Difference is computed as <Active treatment versus Placebo>.

Tier-3 AEs are all other AEs (neither Tier-1 nor Tier-2).

It should be recognized that most studies are not designed to reliably demonstrate a causal relationship between the use of a pharmaceutical product and an adverse event or a group of adverse events. Except for select events in unique situations, studies do not employ formal adjudication procedures for the purpose of event classification. As such, safety analysis is generally considered as an exploratory analysis and its purpose is to generate hypotheses for further investigation. The 3-tier approach facilitates this exploratory analysis.

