To assess the safety and tolerability with a range of DGAT2i doses administered alone, and coadministration of DGAT2i + ACCi, compared to placebo, and the coadministration of DGAT2i + ACCi relative to DGAT2i alone		Assessment of TEAEs, safety- related clinical laboratory tests, vital signs, and 12-lead ECGs, over time up to Week 48
Tertiary/Exploratory:		
To evaluate the effect of a range of DGAT2i doses administered alone, and coadministration of DGAT2i + ACCi, compared to placebo, and the coadministration of DGAT2i + ACCi relative to DGAT2i alone, in participants with worsening of biopsy endpoint components		Proportion of participants with worsening in liver biopsy endpoint components based on assessment by sponsor-identified central pathologist(s) at Week 48 – • Progression of fibrosis by ≥1 stage • Worsening of ≥2 points in Total NAS

For all endpoints, baseline is defined as the evaluable result closest prior to dosing on Day 1/Visit 5

Additional tertiary/exploratory objectives and endpoints are listed in Section 9.4.7.

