7. DISCONTINUATION OF STUDY INTERVENTION AND PARTICIPANT DISCONTINUATION/WITHDRAWAL

7.1. Discontinuation of Study Intervention

In rare instances, it may be necessary for a participant to permanently discontinue study intervention (definitive discontinuation). Reasons for definitive discontinuation of study intervention include participants who meet preidentified thresholds for identified adverse drug reactions with ACCi – refer to Appendix 11 and Appendix 12, as well as other adverse events based on medical judgment, or some other (administrative) reason.

Note that discontinuation of study intervention does not represent withdrawal from the study. Participants can continue in the study and complete all scheduled visits, while off study intervention. If study intervention is definitively discontinued, the participant will remain in

the study to be evaluated for all activities – see the SoA-Table A1 and SoA-Table A2 for data to be collected at the time of discontinuation of study intervention and follow-up for any further evaluations that need to be completed.

In the event of discontinuation of study intervention, it must be documented on the appropriate CRF/in the medical records whether the participant is discontinuing further receipt of study intervention or also from study procedures, posttreatment study follow-up, and/or future collection of additional information.

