9.4.6. Other Safety Analyses

All safety analyses will be performed on the safety population. These will be presented in tabular and/or graphical format and summarized descriptively and will follow Pfizer standards as appropriate.

The MedDRA will be used to classify all AEs with respect to system organ class and preferred term. Summaries of AEs will include treatment-emergent AEs according to treatment group.

Furthermore, a 3-tier approach will be used to summarize AEs. Tier-1 consists of prespecified adverse events of interest and will include AEs or collections of AEs related to identified adverse drug reactions in this program related to either DGAT2i or ACCi. Where available, standard MedDRA queries will be used to pool different AE terms that are related to the Tier-1 AEs. The precise AE terms that will contribute to the Tier-1 endpoints will be determined prior to unblinding. For these events, the percentage of participants with incident AE, the risk difference, its 95% CI, and p-value will be provided. The CI s and p-values are not adjusted for multiplicity and are provided for screening purposes only. Tier-2 AEs are those that are not Tier-1, but are common, occurring in at least 4 participants in any treatment arm. The cut-off of at least 4 events was chosen because the 95% CI for the between-group difference in percent incidence will always include zero when treatment groups of equal size each have less than 4 events and so adds little to the interpretation of potentially meaningful differences. For these events, the percentage of participants with incident AE, the risk difference and its 95% CI will be provided. The CIs are for estimation purposes only. Tier-3 AEs are all other AEs (neither Tier-1 nor Tier-2). For Tier-3 AEs, only within-group incidence proportions will be tabulated.

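### No adverse-event risk difference with a confidence interval is planned for DGAT2i+ACCi versus matching DGAT2i, although the safety objective names that comparison

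*SAP*

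**What the plan says.** The secondary safety objective (Protocol Synopsis and Section 3) has two parts. One sets every active regimen against placebo: "To assess the safety and tolerability with a range of DGAT2i doses administered alone, and coadministration of DGAT2i + ACCi, compared to placebo". The other sets the combination against monotherapy, as in "compared to placebo, and the coadministration of DGAT2i + ACCi relative to DGAT2i alone". Its endpoint covers TEAEs, safety laboratory tests, vital signs and ECGs.

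For AEs, Protocol 9.4.6 promises that "the percentage of participants with incident AE, the risk difference, its 95% CI, and p-value will be provided" for Tier-1 events and names no comparator. SAP 6.6.1 supplies one for Tier-1: "the risk difference (using an unconditional exact test to compare each active treatment arm vs placebo". The Tier-2 sentence in the same section names none, but the example footnote for Tier-1 and Tier-2 output reads "Risk Difference is computed as <Active treatment versus Placebo>".

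Tier-1 is built from identified reactions "related to either DGAT2i or ACCi". Protocol 7.1 refers to "preidentified thresholds for identified adverse drug reactions with ACCi" and points to Appendices 11 and 12, whose titles concern raised fasting triglycerides and falling platelet counts. The Protocol Introduction (Section 2) explains why ACCi alone is not studied.

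For efficacy, SAP 5.2 to 5.2.2 list both matched-dose pairs (150 mg + 5 mg versus 150 mg, and 300 mg + 10 mg versus 300 mg, all BID) and give 90% and 50% CIs for them.

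**The concern.** The plan attaches intervals to the benefit of adding ACCi to DGAT2i but not to its effect on AE incidence. The combination-versus-placebo difference carries the effects of both drugs. The protocol expects DGAT2i to offset part of ACCi's triglyceride effect (Sections 2 and 4.3), so for a lipid-related event the placebo contrast could be small while ACCi still adds events over DGAT2i alone. The results are meant to inform the doses and regimens taken into Phase 3 (Protocol 2.1), and choosing between combination and monotherapy turns on exactly this comparison.

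**Working it through.** **1. The plan's own figure.** SAP 6.6.1 justifies the Tier-2 cut-off of 4 events by stating that, with equal arms and fewer than 4 events in each, the 95% CI for the difference always includes zero. At 50 per arm (SAP 2.2), with Wald limits d ± 1.96·√[p₁(1−p₁)/n + p₂(1−p₂)/n]:
- 3 v 0: 6.0 points, 1.96·√(0.06·0.94/50) = 6.6, so -0.6 to 12.6; exact unconditional p = 0.092.
- 4 v 0: 8.0 points, 1.96·√(0.08·0.92/50) = 7.5, so 0.5 to 15.5; exact unconditional p = 0.0445.

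The cut-off reproduces, and it also does so at 40 and 64 per arm. Nothing in it is specific to placebo.

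**2. Is the missing contrast usable at this size?** At 50 per arm and a common rate p, the half-width is 1.96·√[2p(1−p)/50]. For assumed AE rates of 5%, 10%, 20% and 30% it is 8.5, 11.8, 15.7 and 18.0 points. This is the same precision as an active-versus-placebo contrast at equal rates.

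**3. Illustration.** The counts are assumptions, per 50: placebo 5, DGAT2i 2, combination 9. The variance terms p(1−p)/50 are 0.001800, 0.000768 and 0.002952.

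| Contrast | Difference (points) | Variance | Wald 95% CI (points) |
|---|---|---|---|
| Combination − placebo (planned) | +8 | 0.004752 | -5.5 to 21.5 |
| DGAT2i − placebo (planned) | -6 | 0.002568 | -15.9 to 3.9 |
| Combination − DGAT2i (not planned) | +14 | 0.003720 | 2.0 to 26.0 |

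The point estimate can be recovered from the planned rows: 8 − (−6) = 14. The interval cannot be obtained by treating those rows as independent. Adding their variances gives 0.004752 + 0.002568 = 0.007320, a half-width of 16.8 points and limits of -2.8 to 30.8. That counts the shared placebo variance twice: 0.007320 − 2·0.001800 = 0.003720. The correct interval needs the two arms' counts.

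**4. Other assumed counts.**
- 3, 0 and 6 events, with Miettinen-Nurminen limits and exact unconditional p: combination − placebo +6.0 (-6.0 to 18.8, p = 0.32); combination − DGAT2i +12.0 (4.4 to 23.9, p = 0.012).
- 5, 2 and 6 events, Wald: +2 (-10.3 to 14.3) and +8 (-2.5 to 18.5). Here both intervals include zero.
- 1, 3 and 9 events, Miettinen-Nurminen: +16.0 (5.1 to 29.2) and +12.0 (-0.9 to 25.8). Here the placebo contrast is the larger.

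The two contrasts answer different questions. Which is larger depends on what DGAT2i does to the event.

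**The case against.** A reader might infer that the safety of the combination relative to DGAT2i alone is never estimated, or that the AE tables conceal the difference. The documents support neither reading.

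- SAP 6.3.6 puts fasting triglycerides, platelet count, ALT, AST, ALP, GGT and bilirubin in an MMRM, with 90% CIs for treatment comparisons and additional 50% CIs for each combination dose against its matching DGAT2i dose. Triglycerides and platelets are the two ACCi reactions with preidentified thresholds.
- AE percentages are reported by arm, so the crude difference can be read off and an interval computed from the counts.
- SAP 3.5.2 counts participants crossing triglyceride and platelet thresholds, and SAP 6.6.2 adds individual plots for some of them.
- For Tier-2, placebo-only is an inference: the footnote is introduced as an example and its comparator sits in angle brackets, like a template field.
- No hypothesis tests are planned (Protocol 9.1.2), the safety objective has no stated estimand, and SAP 6.6.1 calls the AE intervals and p-values screening tools within an exploratory analysis.

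All of this stands, and it limits the point to AE incidence and to the interval. It does not remove it. The MMRM estimates mean relative change, not the proportion of participants with an event. It is tertiary/exploratory and uses the Evaluable set with a post-randomisation value, not the Safety set. Post-randomisation changes in lipid medication, which Protocol 6.5.2 allows for, may move mean triglycerides without removing events already recorded. It also covers no other AE. Threshold counts carry no between-arm interval, and leaving readers to compute one is weaker than planning it.

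**Conclusion.** The gap is real but narrow. Part of a stated secondary objective, combination versus DGAT2i alone for TEAEs, has no planned incidence difference with a confidence interval. This is explicit for Tier-1 and implied for Tier-2. Because there is no ACCi-alone arm, the matched-dose pairs are the only direct randomised estimate of ACCi's added effect on AE incidence.

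The consequence is moderate: the data are collected, the percentages are shown, and the analysis is exploratory. The numerical examples rest on assumed counts and 50 per arm. Arm sizes are approximate, since the 150 mg BID comparator also includes participants randomised to 300 mg QD (SAP 2.2). The equal-size reasoning behind the Tier-2 cut-off is then approximate as well.

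**What to change.** In SAP 6.6.1, add Tier-1 and Tier-2 risk differences with 95% CIs, by the method already used for the placebo comparisons, for:
- DGAT2i 150 mg + ACCi 5 mg BID versus DGAT2i 150 mg BID;
- DGAT2i 300 mg + ACCi 10 mg BID versus DGAT2i 300 mg BID.

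Name both comparators in the output footnote, state the Tier-2 comparators in the text, and align Protocol 9.4.6. This should be settled before unblinding, alongside the Tier-1 term list.

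The cost is SAP wording and two more comparison columns in existing tables, with no new data. The statistical price is two further unadjusted contrasts per event, and hence more chance findings, under the screening-only caveat that SAP 6.6.1 already carries.
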